## 6.5 Study Completion/Early Termination Visit

Patients who complete the study or discontinue study drug will be asked to return to the

clinic at 30 ( $\pm$  7) days after the decision to permanently discontinue treatment with fruquintinib. Ongoing AEs will be followed until the event has resolved to baseline grade, the event is assessed as stable by the investigator, new anti-tumor treatment is initiated, the patient is lost to follow-up, the patient withdraws consent, or when it has been determined that the study treatment or participation is not the cause of the AE.

Please see the Study Flowchart provided in [Appendix A](#) for assessments to be performed at the study completion or early termination visit.

## 7 SAFETY PLAN

Patients will be evaluated clinically and with standard laboratory tests before and at regular intervals during their participation in this study. Safety evaluations will consist of medical interviews, recording of AEs, physical examinations, and laboratory measurements.

Except as noted in the current edition of the Investigator's Brochure, no other special warnings or precautions are appropriate.

### 7.1 Adverse Events

#### 7.1.1 Adverse Events

An AE is any unfavorable and unintended sign, symptom, or disease temporally associated with the use of an investigational medicinal product or other protocol-imposed intervention, whether or not considered related to the medicinal product.

Adverse events will be assessed according to the NCI CTCAE v4.03.

#### 7.1.2 Reporting of Dose Limiting Toxicity

Investigators are required to report DLT events to the Sponsor within **48** hours of first awareness, during the dose escalation stage. The communication must include an email that describes the event and indicates which DLT criterion was met (see Section 3.1.1 c, Definition of a Dose-Limiting Toxicity). The Sponsor's medical monitor must confirm that the event meets the DLT definition and communicate this back to the investigator by email. A notification of each DLT event will be distributed by email to all investigators shortly after confirmation. DLT events are again reviewed together with other safety data and PK data, at the SRC meeting upon completion of the DLT window of each dose cohort.

**NOTE:** Reporting of DLTs is not required during the dose expansion phase.

#### 7.1.3 Serious Adverse Events and other AEs that require Expedited Reporting

##### 7.1.3.1 Serious Adverse Event Definition

A serious adverse event (SAE) is any AE that has any of the following characteristics:

- Fatal (ie, the AE actually causes or leads to death, except for deaths caused by the progress of disease)
- Life threatening (ie, the AE, in the view of the investigator, places the patient at immediate risk of death)
- Requires or prolongs inpatient hospitalization (excluding emergency or outpatient treatment)
- Results in persistent or significant disability/incapacity (ie, the AE results in substantial disruption of the patient's ability to conduct normal life functions)

- A congenital anomaly/birth defect in a neonate/infant born to a female patient or female partner of a male patient exposed to the investigational product(s)
- Considered as a significant medical event by the investigator (eg, may jeopardize the patient or may require medical/surgical intervention to prevent one of the outcomes listed above)
- If an AE meets any of the above serious criteria, the AE should be reported to the sponsor as an SAE no more than 24 hours after awareness of the SAE.

### 7.1.3.2 Potential Drug-Induced Liver Injury

The investigator is required to discontinue study drug immediately and report all potential events of drug-induced liver injury (DILI), as defined below, regardless of whether it is a non-serious or serious AE to the sponsor no more than 24 hours after learning of the event.

- Serum AST or ALT  $\geq 3 \times$  ULN together with total bilirubin  $\geq 2 \times$  ULN.

This combination of lab abnormalities meets the biochemical criteria for Hy's law, which is associated with a markedly increased possibility of severe DILI, and may progress to liver transplantation or death. Some patients may present with symptoms such as: fatigue, nausea, vomiting, right upper quadrant pain or tenderness, fever, rash, and/or eosinophilia (>5%). If Hy's law is met, fruquintinib should be immediately discontinued, and patients need to be very closely monitored (bilirubin, ALP, AST, ALT measured 2-3 times weekly until the results return to baseline or normal), and other causes of liver injury evaluated (eg, new or worsening hepatobiliary metastases; non-malignant biliary obstruction; viral hepatitis A, B, or C; alcoholic or autoimmune hepatitis; preexisting or acute liver disease; ischemic liver injury; right-sided congestive heart failure; new or worsening liver metastases; or concomitant medication that could cause the observed injury). Consultation with a gastroenterologist or hepatologist should be considered.

The findings described above must be reported to the sponsor no more than 24 hours after awareness of the event.

### 7.1.3.3 Severe Hemorrhagic Events

When a hemorrhagic event meets NCI CTCAE  $\geq$  Grade 3 severity (regardless of whether it is serious or non-serious), the event should be reported to the sponsor no more than 24 hours after first awareness of the event.

The management of severe or serious hemorrhagic events will be conducted according to [Appendix J](#).

### 7.1.4 Adverse Events Reporting Period

After informed consent, but prior to initiation of study drug, all SAEs regardless of attribution will be collected.

After initiation of study drug, all AEs and SAEs, regardless of attribution will be collected until 30 days following the last dose of study drug or a new treatment of anti-tumor therapy, whichever is earlier. After this period, investigators should report only SAEs that are

considered to be related to the study drug.

### **7.1.5 Eliciting Adverse Events**

A consistent methodology of non-directive questioning for eliciting AEs at all patient evaluation time points should be adopted. Examples of non-directive questions include:

“How have you felt since your last clinic visit?”

“Have you had any new or changed health problems since you were last here?”

### **7.1.6 Assessment of Severity**

Investigators will seek information on AEs and SAEs at each patient contact. All AEs and SAEs, whether reported by the patient or noted by authorized study personnel, will be recorded in the patient’s medical record and on the appropriate AE/SAE form.

For each AE and SAE recorded on the applicable CRF, the investigator will make an assessment of severity through clinical description by referring to the five-grade determination standard in the NCI CTCAE v4.03. Please use the guideline below for the assessment of severity when the observed or reported AE is not listed in the NCI CTCAE v4.03:

- Grade 1: mild; asymptomatic or mild symptoms; clinical or diagnostic observations only; intervention not indicated
- Grade 2: moderate; minimal, local or noninvasive intervention indicated; limiting age-appropriate instrumental activities of daily living (ADL)\*.
- Grade 3: severe or medically significant but not immediately life-threatening; hospitalization or prolongation of hospitalization indicated; disabling; limiting self-care ADL\*\*.
- Grade 4: life-threatening consequences; urgent intervention indicated.
- Grade 5: death related to AE.

## **Activities of Daily Living**

\*Instrumental ADL refer to preparing meals, shopping for groceries or clothes, using the telephone, managing money, etc.

\*\*Self-care ADL refer to bathing, dressing and undressing, feeding self, using the toilet, taking medications, and not bedridden.

### **7.1.7 Causality of Adverse Events**

The investigator will assess causal relationship between study drug and each AE.

For SAEs, a causal relationship will also be assessed for concomitant medications, study procedures and additional study drug, etc. A guideline to the interpretation of causality is provided in [Appendix G](#).

### **7.1.8 Recording Adverse Events**

When an AE or SAE is recorded, the preferred medical terminology or concept should be used. Abbreviations and colloquialisms (eg, jargon or slang) should be avoided. All AEs (including SAEs) should be recorded in the CRF on the AE page.

All AEs (including SAEs) would be recorded on the AE CRF, and the check box for “Serious” would be ticked for entries that fit the criteria for SAEs. The investigator would also complete an SAE report and submit this to the sponsor or its designee within 24 hours of knowledge of the event.

Only one medical concept should be recorded in the event field on the CRF.

#### **7.1.8.1 Diagnosis vs Symptoms and Signs**

If known, a diagnosis should be recorded on the CRF rather than individual signs and symptoms (eg, record only liver failure or hepatitis rather than jaundice, asterixis, and elevated transaminases). However, if a constellation of signs and/or symptoms cannot be medically characterized as a single diagnosis or syndrome at the time of reporting, each individual event should be recorded as an AE or SAE on the CRF. If a diagnosis is subsequently established, it should be reported as follow-up information.

#### **7.1.8.2 Adverse Event Occurring Secondary to Other Events**

In general, AEs occurring secondary to other events (eg, cascade events or clinical sequelae) should be identified by their primary cause with the exception of severe or serious secondary events. For example, if severe diarrhea is known to have resulted in dehydration, it is sufficient to record only diarrhea as an AE or SAE on the CRF if the dehydration is mild.

However, medically significant AEs occurring secondary to an initiating event that are separated in time should be recorded as independent events on the CRF. For example, if a severe gastrointestinal hemorrhage leads to renal failure, both events should be recorded separately on the CRF.

### **7.1.8.3 Persistent or Recurrent Adverse Events**

A persistent AE is one that extends continuously, without resolution between patient evaluation time points. Such events should only be recorded once in the CRF. The event's initial severity should be recorded and updated when it increases so as to record to highest severity.

A recurrent AE is one that occurs, resolves between patient evaluation time points, and subsequently recurs. All recurrent AEs should be recorded on the CRF respectively.

### **7.1.8.4 Abnormal Laboratory Values or Abnormal Vital Signs**

Not every laboratory abnormality/abnormal vital sign qualifies as an AE. A laboratory test result/abnormal vital sign must be reported as an AE if it is a change from baseline and meets any of the following criteria:

- Accompanied by clinical symptoms
- Results in a change in study treatment (eg, dosage modification, treatment interruption, or treatment discontinuation)
- Results in a medical intervention (eg, potassium supplementation for hypokalemia) or a change in concomitant therapy
- Clinically significant in the investigator's judgment

It is the investigator's responsibility to review all laboratory findings and abnormal vital signs. Medical and scientific judgment should be exercised in deciding if an isolated laboratory abnormality should be classified as an adverse event.

If the clinically significant laboratory abnormality is a sign of a disease or syndrome (eg, ALP and bilirubin  $5 \times$  ULN associated with cholecystitis), only the diagnosis (eg, cholecystitis) needs to be recorded on the CRF.

If the clinically significant laboratory abnormality is not a sign of a disease or syndrome, the abnormality itself should be recorded as an AE or SAE on the CRF. If the laboratory abnormality can be characterized by a precise clinical term, the clinical term should be recorded as the AE or SAE. For example, an elevated serum potassium level of 7.0 mmol/L should be recorded as "hyperkalemia."

Observations of the same clinically significant laboratory abnormality from visit to visit should not be repeatedly recorded as AEs or SAEs on the CRF, unless their severity, seriousness, or etiology changes.

### **7.1.8.5 Death**

Deaths that occur during the protocol-specified AE reporting period that are attributed by the investigator solely to progression of disease should not be reported as AE/SAE. All other on-study deaths, regardless of relationship to study drug, must be recorded on the AE CRF and immediately reported to the sponsor. When a death is recorded, the underlying condition that caused or primarily contributed to the fatal outcome should be reported expeditiously as an SAE and death listed as the outcome of the event on the CRF. If the primary cause of death is unknown and cannot be ascertained at the time of reporting,

please record “Unknown cause of death” on the AE CRF, and “unexplained/unknown death” should be expeditiously reported as a SAE before further investigations into the specific cause of death. If the death is attributed to progression of disease, it should not be recorded or reported as an AE/SAE but the investigator will record the death on the End of Treatment and End of Study CRFs as appropriate.

#### **7.1.8.6 Preexisting Medical Condition**

A preexisting medical condition is one that is present at screening. Such conditions should be recorded on the CRF as medical history. A preexisting medical condition should be recorded as an AE or SAE only if the frequency, severity, or character of the condition worsens during the study (excluding deterioration of the study disease conditions). When such events are recorded on the CRF, it is important to convey the concept that the preexisting condition has changed by including applicable descriptors (eg, “more frequent headaches”).

#### **7.1.8.7 Hospitalization, Prolonged Hospitalization, or Surgery**

The investigator must document any AE that results in hospitalization or prolonged hospitalization unless the patient is hospitalized for 1 or more of the following reasons:

- To undergo an efficacy measurement for the study
- To undergo a diagnostic or elective surgical procedure for a preexisting medical condition that has not changed
- To receive scheduled therapy for the target disease of the study

In addition, hospitalization due solely to the progression of underlying advanced solid tumors should not be reported as a SAE.

#### **7.1.8.8 Pregnancy**

A female patient must be instructed to stop taking the study drug and immediately inform the investigator if she becomes pregnant during the study. The investigator should report all pregnancies within 24 hours to the sponsor (the reporting period for pregnancy continues up to 30 days after completion of the study drug). The investigator should counsel the patient and discuss the risks of continuing with the pregnancy and the possible effects on the fetus. Monitoring of the patient should continue until conclusion of the pregnancy. Pregnancies occurring up to 30 days after the completion of the study drug must also be reported to the investigator.

Male patients must also be instructed to inform the investigator immediately if their partner becomes pregnant during the study or within 90 days after the last dose of study drug. If such an event occurs, it should be reported as described above.

Spontaneous abortion should always be classified as serious (as the sponsor considers these medically significant), recorded on the CRF, and expeditiously reported to sponsor.

Any congenital anomaly/birth defect in a child born to a female patient or female partner of a male patient exposed to the investigational product should be recorded and reported as an SAE.

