  10. For female patients of childbearing potential and male patients with partners of childbearing potential, agreement to use a highly effective form(s) of contraception, that results in a low failure rate (<1% per year) when used consistently and correctly, starting during the screening period, continuing throughout the entire study period, and for 90 days after taking the last dose of study drug. Such methods include: oral hormonal contraception (combined estrogen/ progestogen, or progestogen-only), associated with inhibition of ovulation together with a barrier method (eg, diaphragm, always containing a spermicide); intrauterine device (IUD), intrauterine hormone-releasing system (IUS), bilateral tubal ligation, vasectomized partner (on the understanding that this is the only one partner during the whole study duration), or sexual abstinence. Oral contraception should always be combined with an additional contraceptive method (ie, barrier method) because of a potential interaction with the study drug. The same rules are valid for male patients involved in this clinical trial

if they have a partner of childbearing potential. Male patients must always use a condom.

A woman is considered to be of childbearing potential if she is postmenarcheal, has not reached a postmenopausal state (ie,  $\geq 12$  continuous months of amenorrhea with no identified cause other than menopause), and has not undergone surgical sterilization (removal of the ovaries and/or uterus).

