**Table 7 Dose Modification Sequence by Starting Dose**

Starting Dose*	3 mg	5 mg
-1 Dose	2 mg	4 mg
-2 Dose	Off study drug	3 mg
	Only 1 dose reduction is allowed for patients starting at 3 mg QD dose.	A maximum of 2 dose reductions is allowed for patients starting at the 5 mg dose.

\* Doses are daily, on Days 1-21 each 28-day Cycle (3 weeks on, 1 week off)

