### **6.3.3 Laboratory Tests**

Samples for hematology, serum chemistry, urinalysis pregnancy, thyroid function, and specific tumor marker testing will be analyzed at the study site's local laboratory. Laboratory assessments will include the following:

Hematology (complete blood count [CBC], including red blood cell [RBC] count, hemoglobin, hematocrit, reticulocyte count, white blood cell [WBC] count with differential [neutrophils, eosinophils, lymphocytes, monocytes, basophils, and other cells], and platelet count; INR and aPTT);

Serum chemistry (blood urea nitrogen [BUN], creatinine and creatinine clearance, sodium, potassium, chloride, bicarbonate, calcium, magnesium, phosphorus, glucose, triglycerides, total bilirubin, total cholesterol, ALT, AST, alkaline phosphatase (ALP), lactate dehydrogenase [LDH], uric acid, total protein and albumin);

Serum pregnancy test at screening and at the Treatment Completion Visit for all women of childbearing potential, including those who have had a tubal ligation;

Urine pregnancy test at each day 1 visit, starting at Cycle 2 Day 1, for all women of childbearing potential, including those who have had tubal ligation;

Urinalysis (pH, glucose, protein, and blood);

Thyroid function (thyroid stimulating hormone [TSH], free T3, and free T4); and

Specific tumor markers (tumor markers to be collected will be addressed in Section 6.4)

The normal value range of laboratory examination indicators at the study site's local laboratory will be collected prior to the study.

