Date Procedure	Screening		Treatment 							Treatment Completion 	Follow-up
			Cycle 1				Cycle 2-3		Cycle 4 and onwards		
	Day -28 to Day -1	Day -7 to Day -1	Day 1	Day 8 (±1d)	Day 15 (±1d)	Day 22 (±1d)	Day 1 (±3d)	Day 15 (±3d)	Day 1 of each subsequent cycle (±3d)	30 (±7) days after permanent treatment discontinuation	Every 12 (±2) weeks from Treatment Completion Visit
			specific timepoints								
Adverse event 	X	X	X	X	X	X	X	X	X	X	
Fruquintinib treatment			Once daily, 3 weeks on/ 1 week off								
Survival follow up 											X

Note:

1. A written informed consent form should be obtained prior to any protocol-specific procedure or test. Tests completed within 28 days prior to enrollment can be used for screening and do not need to be repeated (except hematology, coagulation test, clinical chemistry, or urinalysis results).
2. Unless otherwise indicated, the visit window during the treatment period will be ± 3 days (± 1 day during cycle 1).
3. Patients who complete or prematurely discontinue the study need to return to the study site for a follow-up at 30 (±7) days after the decision to discontinue treatment permanently. Ongoing AEs will be followed until the event has resolved to baseline grade, the event is assessed as stable by the investigator, new anti-tumor treatment is initiated, the patient is lost to follow-up, the patient withdraws consent, or when it has been determined that the study treatment or participation is not the cause of the AE.
4. The treatment completion visit tumor assessment can be omitted if treatment ended because of disease progression or the patient had a tumor assessment within 14 days prior to the last dose of study drug.
5. Concomitant medication includes any prescribed or over-the-counter medicines. All medication used by patients within 7 days before screening and 30 days after study treatment completion should be recorded. At each visit, all medication used since the prior visit should be recorded.

6. Vital signs include blood pressure, heart rate, respiratory rate, and temperature. For patient with a baseline history of antihypertensive medications, blood pressure should be monitored at 3 hours ( $\pm 2$  hours) after the daily doses of anti-hypertensive medication.
7. Please refer to Section 6.3.2 for the assessments that should be completed as part of the Complete and Limited Physical Exams.

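### Protocol 7.1.8.8 sets a 30-day post-treatment reporting period for pregnancy, while contraception and partner-pregnancy notification run to 90 days

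*Protocol*

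**What the plan says.** Protocol 7.1.8.8 (Pregnancy) gives the investigator 24 hours to report a pregnancy to the sponsor and adds in parentheses that "the reporting period for pregnancy continues up to 30 days after completion of the study drug". The same paragraph ends: "Pregnancies occurring up to 30 days after the completion of the study drug must also be reported to the investigator". It also tells a female patient to stop the drug and "immediately inform the investigator if she becomes pregnant during the study".

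The next paragraph asks male patients to tell the investigator if a partner "becomes pregnant during the study or within 90 days after the last dose of study drug". It then refers back to the preceding paragraph for how such an event is reported.

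Inclusion criterion 10 (Protocol 4.1) requires contraception throughout the study "and for 90 days after taking the last dose of study drug". This applies both to women of childbearing potential and to men with partners of childbearing potential.

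On testing, Protocol 6.3.3 specifies: "Serum pregnancy test at screening and at the Treatment Completion Visit for all women of childbearing potential". Appendix A, note 3, places that visit as a "follow-up at 30 (±7) days after the decision to discontinue treatment permanently". Appendix A, note 13, instead puts the test within 30 days of treatment completion.

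Protocol 7.2 lists pregnancies among the events due to the sponsor within 24 hours and gives that entry no time limit.

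**The concern.** Criterion 10 marks the 90 days after the last dose as a period in which pregnancy must be avoided, and the partner rule uses the same 90 days. The reporting period for the directly exposed woman is the only one of the three set at 30 days. A site that learns of a pregnancy that began on, say, day 60 finds a specific rule saying the period has ended and general rules suggesting it should report anyway.

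A secondary worry is that the last scheduled serum test can itself fall after day 30, so a result from a protocol-mandated test could raise the same question.

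What is at stake is complete and uniform safety reporting of exposed pregnancies. Efficacy, sample size and estimation are not touched. The SAP (17.8.3) only lists individual pregnancy information.

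**Working it through.** **Inputs.** Reporting period: 30 days after completion of study drug (7.1.8.8). Contraception: 90 days after last dose (criterion 10). Partner notification: 90 days after last dose (7.1.8.8). Treatment Completion visit: 30 ± 7 days after the decision to stop (6.5; Appendix A, note 3). Dosing: "Doses are daily, on Days 1-21 each 28-day Cycle" (Table 7 footnote). Scans: Day 1 of a cycle (6.4). The 30 days is a stated window, so there is no calculated figure to reproduce.

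**1. Unmatched interval.** Contraception minus reporting: 90 − 30 = 60 days, i.e. days 31 to 90. Partner notification minus reporting gives the same 60 days. This takes completion of study drug to mean the last dose. If it means the decision to stop, and that decision falls at an on-schedule Day 1 visit 8 days after the last dose (step 3), the period ends at day 8 + 30 = 38 and the gap is 90 − 38 = 52 days.

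**2. Last scheduled test, counted from the decision to stop.** 30 − 7 = day 23 to 30 + 7 = day 37. The latest test is 37 − 30 = 7 days past day 30.

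**3. Last scheduled test, counted from the last dose.**
- Decision on the day of the last dose: days 23 to 37.
- Decision at an on-schedule Day 1 visit: last dose Day 21, next Day 1 = Day 29, gap 29 − 21 = 8 days. The test falls on days 8 + 23 = 31 to 8 + 37 = 45.

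The second case needs a stop exactly at an on-schedule Day 1 visit and a last dose on Day 21. Stops for toxicity, withdrawal of consent or poor compliance (3.6) can fall mid-cycle. Both cases set aside note 13, which conflicts with the ±7-day visit window.

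**4. Other text bearing on days 31 to 90.**
- A woman must report a pregnancy during the study, and patients are followed to death or study completion (3.1.1, 3.1.2). SAP 2.1 ties study completion to the End of Study form.
- 7.2 requires the 24-hour report of pregnancies and sets no limit.
- 7.3 asks that pregnancies during the study be followed to outcome.
- Spontaneous abortions and birth defects are reportable under 7.1.8.8 with no stated window. Drug-related SAEs are reportable after 30 days (7.1.4, 7.2).

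These cover many cases. They do not cancel a sentence that names a reporting period and ends it at 30 days.

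**5. Pharmacology, for scale.** Protocol 1.3.1 gives a terminal half-life above 35 hours. Thirty days is 720 hours: 720 / 35 = 20.6 half-lives at 35 hours, and 720 / 70 = 10.3 at an assumed 70 hours.

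**The case against.** The strongest reply is that little is lost in practice. A woman in follow-up at day 60 is normally still on study, so she must tell the investigator, who must then report under 7.2. The second 30-day sentence can be read as adding a duty and not as ending one. The 30 days also looks deliberate: Appendix K (Amendment 2) records it as a clarification of duration, and it matches the 30-day adverse event period in 7.1.4. Nothing in the protocol says contraception and reporting periods must be equal.

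Much of this stands, and it rules out several stronger readings that a reader might infer.

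- *Pregnancies after day 30 go unreported or may not be reported.* The documents do not say so. The general duties in step 4 of the working point the other way, with patients who leave the study early least covered.
- *Partner pregnancies on days 31 to 90 are excluded from sponsor reporting.* The back-reference can equally be read as sponsor reporting through day 90. The fair description is unclear.
- *The last pregnancy test routinely falls outside the window.* That depends on the conditions in step 3 and on disregarding note 13. The second 30-day sentence also speaks of when a pregnancy occurs, so one detected on day 37 may have begun inside the window. The text does not say whether conception or detection governs.
- *Drug exposure makes 90 days necessary.* On the half-life given, 30 days is already many half-lives.

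The objection does not remove the plain mismatch. If the duty during the study already covered all of follow-up, the 30-day statements would have no work to do. A site should not have to choose between the specific rule and the general ones.

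**Conclusion.** The inconsistency is real and minor. For female patients, 60 days (days 31 to 90 after the last dose) lie outside the specific reporting period while contraception is still required. The figure is 52 days if completion of study drug means a stop decision made at an on-schedule Day 1 visit. For partner pregnancies, only the onward report to the sponsor over those days is unclear.

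The test-timing point is secondary: up to 7 days past day 30 counted from the decision to stop, and possibly later counted from the last dose, with note 13 in conflict.

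The number of women of childbearing potential is not given, so the number of patients affected is unknown and may be zero. The case for change rests on consistency with the 90 days the protocol already chose, and it is a cheap improvement.

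**What to change.** In Protocol 7.1.8.8, change both 30-day statements to 90 days after the last dose of study drug. Add one sentence saying that the 24-hour report to the sponsor applies to both patient and partner pregnancies through that period. The latest test date in step 3 (day 45) would then lie well inside the window, so the conflict with note 13 would no longer matter for reporting.

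Leave the pregnancy entry in 7.2 without a time limit, or cross-refer to 7.1.8.8 without restricting it. Writing a window beside it would narrow a duty that now has none. A pregnancy question at the survival call is not worth adding. The first call comes 12 ± 2 weeks after the Treatment Completion visit, so at the earliest on day 23 + 70 = 93 after the decision to stop, and note 17 provides it only for Cohorts B to E.

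Cost: two changed windows and one sentence, with no new visit, call or test. Downside: pregnancy reporting runs 90 − 30 = 60 days longer than the adverse event period.
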